## List of abbreviations

BCG:	Bacillus Calmette-Guérin
CI:	Credible Interval
eCRF:	electronic Case Report Form
ICU:	Intensive Care Unit
IQR:	Inter Quartile Range
RCT:	Randomised Controlled Trial
SD:	Standard deviation
UMCU:	University Medical Center Utrecht

---

# 1 Overview of the study

---

*This is a copy of the protocol summary, version 3.0, 01-April-2020:*

**Rationale:** SARS-CoV-2 spreads rapidly throughout the world. A large epidemic in the Netherlands would seriously challenge the available hospital capacity, and this would be augmented by absenteeism of healthcare workers (HCW). Strategies to prevent absenteeism of HCW are, therefore, desperately needed to safeguard continuous patient care. Bacille Calmette-Guérin (BCG) is a vaccine against tuberculosis, with protective non-specific effects against other respiratory tract infections in *in vitro* and *in vivo* studies, and reported significant reductions in morbidity and mortality. We hypothesize that BCG vaccination can reduce HCW absenteeism during the epidemic phase of SARS-CoV-2.

**Objective:** Primary objective: To reduce absenteeism among HCW with direct patient contacts during the epidemic phase of COVID19. Secondary objective: To reduce hospital admission, ICU admission or death in HCW with direct patient contacts during the epidemic phase of COVID19.

**Study design:** A placebo-controlled adaptive multi-centre randomized controlled trial.

**Study population:** HCW with direct patient contacts, defined as nurses and physicians working at emergency rooms and wards where COVID-infected patients are treated.

**Intervention:** Participants will be randomized between intracutaneous administration of BCG vaccine or placebo in a 1:1 ratio.

**Main study parameters/endpoints:** Primary endpoint: number of days of (unplanned) absenteeism for any reason. Secondary endpoints: number of days of (unplanned) absenteeism because of documented SARS-CoV-2 infection, and the cumulative incidence of hospital admission, Intensive Care Admission, and death.

**Nature and extent of the burden and risks associated with participation, benefit and group relatedness:** Based on previous experience and randomized controlled trials in adult and elderly individuals, the risks of BCG vaccination are considered low. The objective of this trial is to evaluate the beneficial effects of BCG vaccination through a lower work absenteeism rate of HCW and/or a mitigated clinical course of SARS-CoV-2 infection. The primary endpoint and the adaptive design with frequent interim analyses facilitate maximum efficiency of the trial, so that results can inform policy making during the ongoing epidemic.

---

## **2 Sample size determination**

---

The aim is to enrol a total of 1500 HCW (750 BCG and 750 placebo). For a detailed sample size calculation, please refer to the protocol.

---

## 3 Definitions

---

### 3.1 Treatment groups

BCG: participants randomised to receive BCG

Placebo: participants randomised to receive placebo

### 3.2 Analysed populations

The primary analysis population is the intention-to-treat (ITT) population in which participants will be analysed according to the random allocation.

#### **Subgroups:**

No subgroups have been predefined.

### 3.3 Study definitions

COVID-19 disease is defined as respiratory tract symptoms or fever in combination with PCR-based detection of SARS-CoV-2 in a respiratory sample.

SARS-CoV-2: severe acute respiratory syndrome coronavirus-2. The virus that causes COVID-19 disease.

---

## 4 General statistical considerations

---

### 4.1 General statistical methodology

The methodology presented in this statistical analysis plan takes into account methods planned in the protocol, specifies them, and completes them. The analysis will be performed in the statistical software R. The version of R and R libraries used will be reported.

### 4.2 Handling of missing data

For analyses of primary or secondary endpoints with missing data, multiple imputed data analysis will be performed using Multivariate Imputation by Chained Equations; complete data analysis will be performed as a sensitivity analysis to check for inconsistencies. Missing outcome data will not be imputed.

### 4.3 Descriptive statistics

According to the variable type, descriptive statistics will be:

- Quantitative criteria: number of observations (N), mean, standard deviation (SD), median and interquartile range (IQR), as applicable.
- Qualitative criteria: number of observations (N), absolute frequency (n) and relative frequency (%). Percentages will be calculated on the number of participants with documented data.

### 4.4 Inferential statistics

Bayesian analysis will be used for inferential statistics. Effect estimates for primary and secondary endpoints will be reported with 95% credible intervals (CI). For the primary endpoint, a 99% CI as well as the posterior probability of superiority and futility will be reported in addition to the 95% CI, in line with the interim analysis.

---

## **5 Disposition of participants and conduct of the study**

---

### **5.1 Participant disposition and size of the analysed populations**

The study flowchart will describe:

- Number of subjects screened
- Number of subjects not meeting the eligibility criteria
  - o Reasons for non-eligibility
- Number of subjects eligible but not included
  - o Reasons for non-inclusion
- Number of participants included and randomised
- Early termination: Number of participants withdrawn, dropouts
  - o Reasons for early termination

### **5.2 Conduct of the study**

The following will be reported on the conduct of the study:

- Enrolment period: date First Patient First Visit – date Last Patient First Visit
- Distribution of actual duration of follow-up per participant by treatment arm
- Number and proportion of days with missing outcome measurement by treatment arm

## 6 Demographics and other baseline characteristics

### 6.1 Demographics / baseline characteristics

The following data will be described for included participants by treatment arm and for the total population:

VARIABLE	DERIVATION	STATISTICAL METHOD *
Age (years)	Self-reported; baseline eCRF	Median (IQR) or mean (sd) 
Gender	Self-reported; baseline eCRF: Male/ Female	n/N (%)
History of BCG vaccination	Self-reported; baseline eCRF: Yes/No	n/N (%)
Age at BCG vaccination	Self-reported; baseline eCRF	Median (IQR) or mean (sd)  among those with reported history of BCG vaccination
History of positive Mantoux test	Self-reported; baseline eCRF. Options are: - Yes - No; at least one negative test - No; never tested Answer option "I don't know" will be handled as missing value	n/N (%) for all categories
History of positive TB quantiferon test	Self-reported; baseline eCRF. Options are: - Yes - No; at least one negative test - No; never tested Answer option "I don't know" will be handled as missing value	n/N (%) for all categories
Receipt of influenza vaccination in past season	Self-reported; baseline eCRF: Yes/No	n/N (%)
Receipt of other vaccinations in past 12 months	Self-reported; baseline eCRF (open question) 	n/N (%) for each reported vaccination
History of respiratory tract infection in past winter	Self-reported; baseline eCRF. Options are: - Yes, with fever - Yes, without fever - No	n/N (%) for all categories:
Use of anti-hypertensive medication	Self-reported; baseline eCRF: Yes/No	n/N (%)
History of cardiovascular disease	Self-reported; baseline eCRF: Yes/No	n/N (%)
Use of anti-diabetic medication	Self-reported; baseline eCRF: Yes/No	n/N (%)
History of asthma	Self-reported; baseline eCRF: Yes/No	n/N (%)
History of other pulmonary diseases	Self-reported; baseline eCRF (open question) 	n/N (%) for each reported pulmonary disease

History of smoking	Self-reported; baseline eCRF. Options are: - Never smoked - Ever smoked - Current smoking	n/N (%) for all categories
History of allergic rhinitis	Self-reported; baseline eCRF: Yes/No	n/N (%)
Number of household members	Self-reported; baseline eCRF	Median (IQR) or mean (sd) 
Age of household members	Self-reported; baseline eCRF	n/N (%) with household members < 18 n/N (%) with household members >= 18 and < 50 n/N (%) with household members >= 50
Department of employment	Self-reported; baseline eCRF. Options are: - Intensive care - Medium care - Emergency room - Internal medicine - Infectious diseases - Pulmonary diseases - Other, specify (open question) 	n/N (%) for all categories
Position at department of employment	Self-reported; baseline eCRF. Options are: - Nurse - Medical doctor - Paramedical - Supportive - Secretary	n/N (%) for all categories
Current or planned deployment in dedicated COVID-19 department	Self-reported; baseline eCRF. Yes/No Answer option "I don't know" will be handled as missing value	n/N (%)
Average number of working days in the hospital	Self-reported; baseline eCRF.	Median (IQR) or mean (sd) 
Average number of working days on evening/night shift	Self-reported; baseline eCRF.	Median (IQR) or mean (sd) 
Percentage of working time spend with direct patient contact	Self-reported; baseline eCRF. Options are: - ≤25% - 26-50% - 51-75% - >75%	n/N (%) for all categories
Has at least one day of work loss due to illness between 1 January and 15	Self-reported; baseline eCRF. Options are:	n/N (%) for all categories

March 2020	- Yes, due to respiratory tract infection - Yes, for alternative health issue - No	
Total days of work loss due to illness between 1 January and 15 March 2020	Self-reported; baseline eCRF.	Median (IQR) or mean (sd)  among those with reported work loss due to illness
Previously tested for COVID-19	Self-reported; baseline eCRF. Options are: - No - Yes, negative test result - Yes, positive test result	n/N (%) for all categories
Number of days since negative test	Self-reported; baseline eCRF. Date negative test minus date of enrolment.	Median (IQR) or mean (sd)  among those with reported negative test result
Number of days since positive test	Self-reported; baseline eCRF. Date positive test minus date of enrolment.	Median (IQR) or mean (sd)  among those with reported positive test result
Has had negative COVID-19 test after being tested positive	Self-reported; baseline eCRF. Yes / No	n/N (%)
Number of days since negative test after being tested positive	Self-reported; baseline eCRF. Date negative test minus date of enrolment.	Median (IQR) or mean (sd)  among those with reported negative test result after being tested positive

\* It will not be statistically tested whether baseline characteristics differ by treatment arm.

1. The description method will depend on the normality of the data.
2. Open questions will be categorized by the coordinating investigator.

---

## 7 Analysis of the primary endpoint

---

The primary endpoint, work absenteeism for any reason, will be reported as the average proportion of sick-days with standard deviation by treatment arm. It will be analysed as total counts (i.e. one observation per participant) using a Bayesian negative binomial regression with a fixed effect for BCG, hospital, enrolment week (categorical), age, department (whether planned to work on COVID-19 dedicated department), sick leave prior to enrolment (as a proportion of fte), and presence of at least one of four comorbidities: cardiovascular disease, use of anti-diabetic medication, asthma, pulmonary diseases. Age and prior sick leave will be modelled using a spline function. The total number of planned workdays for the respective person over the follow-up period will be used as offset (log-transformed). The brm function from the R package brms will be used for fitting the negative binomial model.

The effect will be reported as a relative risk with 95% and 99% CI. The posterior probability for the superiority hypothesis ( $RR < 1$ ) will be reported as well as the posterior probability for the futility hypothesis ( $RR > 0.8$ ).

Model assumptions will be checked using residuals plots and rootograms and posterior distribution plots will be presented. If model assumptions are violated, the following alternative model will be used: analysis as sick/non-sick working days (i.e. multiple observation per participant, one observation for each planned working day) using a Bayesian logistic regression model with a random intercept per participant, a fixed effect for BCG, hospital, observation week (categorical), age, department (whether planned to work on COVID-19 dedicated department), sick leave prior to enrolment (as a proportion of fte), and presence of at least one of four comorbidities: cardiovascular disease, use of anti-diabetic medication, asthma, other pulmonary diseases. Age and prior sick leave will be modelled using a spline function. An autocorrelation structure of 1st order over time within participants will be added. This model yields an odds ratio (OR) which can be interpreted as RR if the risk of sick leave is <10% and will be used for determination of superiority or futility in the same manner as planned for the RR.

The same modelling approach will be used during interim analyses. Please refer to section 10: Interim analysis for a description.

---

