## 10 Interim analyses

---

Interim analyses will be performed starting from 4 weeks after the first enrolled patient and subsequently every 2 weeks. The interim analysis will be performed by the trial statistician unblinded and will not be disclosed to other study team members. Monthly, the results will be provided to the DSMB unblinded. In case of suggested futility or efficacy, the DSMB statistician will independently replicate the full data analysis before drawing conclusions.

The disposition of participants and conduct of the study will be analysed and reported (section 5).

Of the baseline characteristics (section 6), the following will be reported during the interim analysis:

- Hospital of employment
- Age
- Gender
- History of BCG vaccination
- Department of employment
- Whether planned to work on COVID-19 dedicated department
- Position at department of employment
- Average number of working days in the hospital
- Total days of work loss due to illness between 1 January and 15 March 2020

The following endpoints will be analysed and reported in the same way as described in the above sections:

- Primary endpoint, work absenteeism for any reason (section 7). If during any of the interim analyses, the posterior probability of superiority is  $> 0.995$  or the posterior probability of futility is  $> 0.99$ , a conclusion is reached. In case of superiority, the trial will be stopped. In case of futility, the DSMB will take the totality of the data into account in their recommendation to continue or stop the trial.
- Hospital admission due to COVID-19 (section 8.13)
- SAEs and SUSARs (section 9.1)

Please also refer to the DSMB charter for roles and responsibilities and organizational aspects.

---

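### Does section 7 of the SAP quietly change the primary endpoint from absence for any reason to absence through sickness?

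*SAP*

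**What the plan says.** SAP section 1 gives the primary endpoint as days of absenteeism for any reason, with the word *unplanned* in brackets. Section 7 begins: "The primary endpoint, work absenteeism for any reason, will be reported as the average proportion of sick-days with standard deviation by treatment arm". The main model then takes that endpoint as one total count per participant, in a Bayesian negative binomial regression with log planned workdays as offset. Nothing in the description of that outcome refers to sickness.

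If the model assumptions are violated, section 7 moves to a logistic model: "analysis as sick/non-sick working days (i.e. multiple observation per participant, one observation for each planned working day"). On its effect measure the section says "This model yields an odds ratio (OR) which can be interpreted as RR if the risk of sick leave is <10" per cent, and that it "will be used for determination of superiority or futility in the same manner as planned for the RR". It adds: "The same modelling approach will be used during interim analyses".

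Section 10 lists the interim outcome as "Primary endpoint, work absenteeism for any reason (section 7"), with a superiority threshold of 0.995 and a futility threshold of 0.99 on the posterior probabilities. The consequences differ: "In case of superiority, the trial will be stopped", whereas "In case of futility, the DSMB will take the totality of the data into account".

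Section 3.3 defines neither absenteeism nor a sick-day.

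**The concern.** Absence for any reason and absence through sickness are different quantities, and the SAP itself recognises absence that need not involve illness: section 9.2.1 covers quarantine after exposure, listed apart from quarantine for symptoms, fever or infection in 9.2.2. Three parts of section 7 use sickness words: the descriptive summary, the fallback outcome, and the risk that must lie below 10% for the odds ratio to stand in for a relative risk. No definition equates the terms.

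Taken literally, this has two consequences. The proportion reported by arm would not describe the outcome that the main model analyses. And if the model check failed, the outcome would change together with the model. Since the fallback serves the interim rules as well, a trial could in principle be stopped for superiority on a narrower endpoint than the one declared.

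**Working it through.** **1. The wording in context.** The SAP states no figure on this point that could be reproduced, so the first check is of the text.

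| Place in the SAP | Wording of the outcome | What the context shows |
|---|---|---|
| Section 1 | any reason | declares the endpoint |
| Section 7, summary | any reason, reported in sick-days | one subject; sick-days are its reporting unit |
| Section 7, main model | total counts of that same endpoint | no sickness wording |
| Section 7, fallback | sick/non-sick working days | offered as an alternative model; the bracket explains the data structure (several observations per person), as the bracket after the count model does (one per person) |
| Section 7, OR condition | risk of sick leave | the risk of the outcome just described |
| Section 9.2.1 | quarantine after exposure | uses the primary endpoint's modelling approach |
| Section 10 | any reason, referring to section 7 | the outcome for the stopping rules |

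The shorthand reading fits every row. The literal reading makes the opening sentence of section 7 contradict itself, sets the fallback against section 10, and leaves the fallback unsuitable for 9.2.1.

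**2. What the literal reading could do (hypothetical).**

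*From the SAP:* superiority if P(RR < 1) > 0.995; futility if P(RR > 0.8) > 0.99; 750 per arm.

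*Assumed, not in the SAP:* the model check fails; *sick* is read literally; a share q of placebo absence is quarantine without illness that counts towards the endpoint; BCG has no effect on those days; the estimated sick-day RR is r = 0.75; the posterior for log RR is normal with a flat prior and the same SE for both outcomes.

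RR on any-reason absence = r(1 − q) + q:
- q = 10%: 0.75 × 0.9 + 0.1 = 0.775
- q = 20%: 0.75 × 0.8 + 0.2 = 0.80
- q = 50%: 0.75 × 0.5 + 0.5 = 0.875

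P(RR < 1) = Φ(−ln RR / SE):

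| SE | sick-days (0.75) | q = 10% | q = 20% | q = 50% | Does the superiority decision differ? |
|---|---|---|---|---|---|
| 0.05 | > 0.995 | > 0.995 | > 0.995 | 0.9962 | no, all meet the rule |
| 0.10 | 0.9980 | 0.9946 | 0.9872 | 0.9091 | yes |
| 0.15 | 0.9724 | 0.9554 | 0.9316 | 0.8133 | no, none meets it |

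At SE 0.10 the superiority boundary is exp(−2.576 × 0.10) = 0.773, so the chosen 0.75 lies just inside it. Futility needs RR > 0.8 × exp(2.326 × 0.10) = 1.010. Expressed as a sick-day RR, any-reason absence would need more than 1.011, 1.012 or 1.019 at q = 10, 20 or 50%, so the futility rule hardly moves.

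*Where SE 0.10 comes from:* SE = √[(1/m + 1/k + 1/(0.8m) + 1/k)/750], with m the mean days absent on placebo and k the negative binomial dispersion parameter, both assumed. With m = 2 and k = 0.3: √[(0.5 + 3.333 + 0.625 + 3.333)/750] = 0.102. Over m = 1 to 5 and k = 0.1 to 1 the SE runs from 0.057 to 0.172. This formula belongs to the model that the scenario supposes has been rejected, and sick-days, as a subset of absence, need not share its SE.

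**3. The 10% condition.** A true RR of 0.8 corresponds to a marginal OR of 0.792 at a placebo risk of 5%, 0.783 at 10% and 0.773 at 15%. Which risk is compared with 10% therefore matters only modestly to the approximation, and on the shorthand reading it is simply the risk of absence.

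**The case for a change.** The strongest case for a change is about replication. Section 10 has the DSMB statistician independently repeat the full analysis when futility or efficacy is suggested, and two analysts should not have to guess how to code a sick day. Section 7 also seems to use *sick leave* literally for the covariate before enrolment, since the matching baseline items in section 6.1 ask about work lost to illness. One phrase may thus carry two meanings in the same section. A definition of absenteeism in the protocol would not alter the SAP's words, and changing three terms would cost almost nothing.

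The factual part stands: the terms are inconsistent and the SAP does not equate them. What does not stand is that competent analysts would be led astray. The endpoint is named in the sentence that introduces the summary and again where the interim rules are set out, and a fallback on sickness alone would contradict both. The prior-leave covariate is a baseline variable with its own source and does not bear on the outcome.

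Whether quarantine days count as unplanned absence is a separate question. It concerns the definition of the endpoint, which a SAP commonly leaves to the protocol, and the protocol is not at hand. It cannot be held against the SAP's wording.

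**Conclusion.** This is a clerical slip in terminology. *Sick* in section 7 most probably stands for *absent*, and analysts who follow the named endpoint would code it so without instruction. The main model is not affected on either reading.

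On the probable reading the effect on results is nil: what remains is a loose label on the descriptive summary and loose wording of the fallback. On the literal reading the size is unknown, since the SAP gives no share of absence without illness, no mean and no dispersion. The illustration changes the superiority decision only if a failed model check, a literal reading, quarantine counted in the endpoint, no vaccine effect on those days and an SE near 0.10 all coincide. It shows what is conceivable and is not evidence of impact. Tidier wording would not alter any planned analysis, so no change to the plan follows.

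The conclusion rests on reading section 7 together with sections 9.2.1 and 10; the protocol's definition of absenteeism was not available.

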### **8.1 number of days of unplanned absenteeism, because of COVID-19 disease**

The same modelling approach will be used as for the primary endpoint.

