### 9.3 Days with symptoms endpoints

For the following endpoints, the same modelling approach will be used as for the primary endpoint.

- 9.3.1 number of days of self-reported fever ( $\geq 38$  °C)
- 9.3.2 number of days of self-reported acute respiratory symptoms

For the following endpoints, the same modelling approach will be used as for endpoint 8.2 Cumulative incidence of COVID-19 disease

- 9.3.3 the cumulative incidence of self-reported fever ( $\geq 38$  °C)
- 9.3.4 the cumulative incidence of self-reported acute respiratory symptoms

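### The primary model's offset is not limited to workdays with a recorded outcome, so unrecorded workdays may in effect be counted as worked

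*SAP*

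**What the plan says.** - **Primary model (SAP section 7).** On the outcome: "It will be analysed as total counts (i.e. one observation per participant) using a Bayesian negative binomial regression". On the exposure: "The total number of planned workdays for the respective person over the follow-up period will be used as offset (log-transformed". The endpoint is also reported as a mean proportion of sick-days by arm; the denominator of that proportion is not defined separately.
- **Fallback model (section 7).** If model assumptions fail, a Bayesian logistic model is used with "multiple observation per participant, one observation for each planned working day". Its odds ratio then serves the same superiority and futility decisions as the RR.
- **Missing data (section 4.2).** Multiple imputation is planned, but "Missing outcome data will not be imputed". Imputation can therefore reach covariates only.
- **Conduct (section 5.2).** The report will include "Number and proportion of days with missing outcome measurement by treatment arm", and the actual length of follow-up by arm. For the interims, section 10 adds: "The disposition of participants and conduct of the study will be analysed and reported (section 5".
- **Reuse.** Section 8.1 states "The same modelling approach will be used as for the primary endpoint", and section 9.2 says the same. For the day counts in section 9.3: "For the following endpoints, the same modelling approach will be used as for the primary endpoint".

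**The concern.** A rate model needs its count and its exposure to cover the same days. Here the count can only contain sick days that somebody recorded, while the exposure is every planned workday. A planned workday without a record then lengthens the exposure and adds nothing to the count, which is arithmetically the same as a day worked. That amounts to a silent single imputation of attendance, and it sits badly with the rule that outcomes are not imputed.

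Two things are at stake. The absence proportions would be too low in both arms. And if the arms differ in how many workdays go unrecorded, the RR would shift in a direction set by reporting behaviour. The same model drives the interim rules, where superiority stops the trial. The section 5.2 table would show an imbalance in missing days to those reading the interim report, but it would not correct the RR.

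**Working it through.** **Inputs.** From the SAP: 750 per arm (section 2); hypotheses RR < 1 and RR > 0.8 (section 7); thresholds 0.995 and 0.99 (section 10). Assumed, because the SAP gives no values: missing shares, 5% absence, mean sick days per person (mu) 3 to 8, dispersion (k) 0.3 to 1. The plan states no figure on this point, so there is none to reproduce.

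**Step 1, level.** With absence risk p and an unrecorded share m unrelated to sickness, recorded sick days per planned day are p(1 − m). For p = 0.05 and m = 0.10: 0.05 × 0.90 = 0.045, so 4.5% on planned days. On recorded days, 0.045/0.90 = 5.0%.

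**Step 2, RR.** The planned-day offset multiplies the RR by (1 − m_BCG)/(1 − m_placebo). A recorded-day offset multiplies it by 1.

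| Unrecorded, BCG vs placebo | Factor on RR |
|---|---|
| 10% vs 10% | 0.90/0.90 = 1.000 |
| 11% vs 9% | 0.89/0.91 = 0.978 |
| 15% vs 10% | 0.85/0.90 = 0.944 |
| 10% vs 15% | 0.90/0.85 = 1.059 |

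**Step 3, check by simulation.** 300 trials per scenario, 750 per arm, true RR 1, 100 planned days, 5% absence, k = 0.5, maximum-likelihood negative binomial fit, Monte Carlo SE about 0.004. Planned-day offset: 0.982 (11% vs 9%), 0.942 (15% vs 10%), 1.054 (10% vs 15%), 1.006 (10% each). Recorded-day offset: 1.003, 0.997, 0.996, 1.005.

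**Step 4, one look at the thresholds.** Normal approximation with a weak prior: SE = sqrt(2(1/mu + 1/k)/n). With n = 750 this runs from 0.055 (mu 8, k 1) to 0.099 (mu 3, k 0.3).
- At true RR 1, the chance that P(RR < 1) exceeds 0.995 is Phi(−ln(factor)/SE − 2.576). Without imbalance it is 0.5%. With 11% vs 9% it is 0.9–1.5%; with 15% vs 10% it is 2.3–6.3%.
- At true RR 0.8, the chance that P(RR > 0.8) exceeds 0.99 is Phi(ln(factor)/SE − 2.326). Without imbalance it is 1%. With 9% vs 11% it is 1.8–2.7%; with 10% vs 15% it is 4.0–10.0%.
- With 150 per arm (mu 1 to 3, SE 0.133–0.240), the 5-point gap gives only 1.0–1.6% and 1.8–2.9%.

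**Step 5, missingness that depends on sickness.** Let ms and mw be the unrecorded shares of sick and well days. The planned-day rate is p(1 − ms). The recorded-day rate is p(1 − ms)/[p(1 − ms) + (1 − p)(1 − mw)]. With p = 0.05 in both arms, so true RR 1:

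| Unrecorded days (BCG vs placebo) | Planned-day RR | Recorded-day RR |
|---|---|---|
| All days, 15% vs 10% | 0.944 | 1.000 |
| Well days 15% vs 10%, sick days 10% in both | 1.000 | 1.056 |
| Sick days 15% vs 10%, well days 10% in both | 0.944 | 0.947 |

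**Step 6, the two models side by side.** In the count model an unrecorded planned workday stays in the offset. In the day-level model it would be a row with no outcome; without imputation, such a row contributes nothing to the likelihood.

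**The case against.** The strongest reply is that the outcome depends on how planned workdays are captured, which the SAP does not describe and may leave to the protocol. If participants report for each day whether they were scheduled and whether they attended, a planned workday is known only when it is reported. Count and offset then match and nothing is wrong. This stands as a possible reading, but the SAP does not state it. A third reading, in which any missing day makes the whole total missing and removes the participant, is not stated either, and it too would differ from the fallback.

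Three stronger conclusions are tempting and should not be drawn:
- *That the SAP declares an unrecorded day to be a day worked.* It does not. This follows only if planned workdays are known separately and the total sums recorded sick days.
- *That the two models contradict each other.* The fallback's omission of such days is inferred. Its text, taken literally, also gives every planned workday a row.
- *That the RR will be biased.* Equal missingness unrelated to sickness leaves it unchanged. The trial is randomised and placebo-controlled, and nothing in the SAP predicts an imbalance.

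It is also fair to say that a recorded-day offset is not better under every mechanism; Step 5 shows one in which the planned-day offset does better.

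**Conclusion.** The point holds conditionally and should be settled in the text. Section 7 fixes an exposure that, as worded, need not match the count, in a plan that expects missing outcome days and does not impute them. Under the two conditions named above, absence proportions are too low by the factor (1 − m), whatever the balance between arms. The RR is affected when the unrecorded share differs by arm: about 2% for an assumed 2-point gap and about 6% for an assumed 5-point gap, in either direction. The threshold probabilities are for one look near full enrolment and rest on assumed missingness, mean days and dispersion; they show sensitivity and do not forecast error rates. If follow-up in the offset means scheduled rather than actual follow-up, days after dropout would add to the mismatch; if it means actual follow-up, only gaps within it matter.

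**What to change.** 1. Define the count, the offset and the denominator of the reported proportion on one set of days: planned workdays within actual follow-up that have a recorded attendance outcome.
2. Use that set in the fallback model, at every interim, and for 8.1 and 9.2. For the day counts in 9.3, use days with a recorded symptom outcome.
3. Exclude participants with no recorded workday, whose log offset is undefined, and report their number by arm.
4. Where unrecorded planned workdays are known, report the planned-day offset as a simple sensitivity analysis, because the recorded-day offset does not correct missingness that depends on sickness.

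If planned workdays are already counted only on reported days within actual follow-up, one sentence saying so settles the definition.

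**Cost.** SAP wording, one derived variable and one extra fit. The sensitivity analysis needs the number of unrecorded planned workdays; the section 5.2 table counts days with missing outcome, which is not the same thing. Exposure falls slightly. Absolute absence may be overstated if well participants skip reports: with a true 5%, and 5% of sick and 15% of well days unrecorded, the recorded-day proportion is 0.0475/0.855 = 5.56%, against 4.75% on planned days.
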